8.8 Chain of Custody of Biological Samples

A full chain of custody is maintained for all samples throughout their lifecycle. The Principal Investigator at each center keeps full traceability of collected biological samples from the patients

while in storage at the center until shipment or disposal (where appropriate) and keeps documentation of receipt of arrival. The Principal Investigator will also ensure that access to the samples while in storage at the study center will be limited only to those people for whom access is required. The sample receiver keeps full traceability of the samples while in storage and during use until used or disposed of or until further shipment and keeps documentation of receipt of arrival. Aprea Therapeutics AB keeps oversight of the entire life cycle through internal procedures, monitoring of study sites and auditing of external laboratory providers. Samples retained for further use will be registered in the Aprea Therapeutics AB biobank system during the entire life cycle. Samples will be stored for up to 15 years.

8.9 Withdrawal of Informed Consent for Donated Biological Samples

If a patient withdraws consent to the use of voluntarily donated biological samples, then the samples will be disposed of/destroyed, and the action documented. If samples are already analyzed, Aprea Therapeutics AB is not obliged to destroy the results of this research. As collection of the genetic blood sample is a voluntary part of the study then the patient may continue in the study.

9.0 STATISTICS

9.1 Primary Endpoint

The primary endpoint is progression-free survival (PFS) based on BICR and is defined as the number of days from the date of randomization to the date of objective disease progression or relapse (according to RECIST v1.1 only) or death due to any cause, whichever occurs first. If neither event occurs, PFS will be censored at the date of the last evaluable tumor assessment. Symptomatic deterioration is not objective disease progression.

9.2 Secondary Endpoints

Secondary endpoints include:

- Best overall response and overall response rate (according to RECIST v1.1 and GCIG Criteria)
- Duration of response (complete or partial response)
- PFS by assessment of CA-125 (according to GCIG Criteria)
- Overall survival
- Safety profile based on AEs and laboratory assessments
- Evaluation of biomarkers and tumor activity based on CA-125
- Quality of Life assessment using EORTC Ovarian (QLQ-30 and QLQ-OV28) and the Functional Assessment of Cancer Therapy-Ovarian (FACT-O)

9.3 Sample Size

Adaptive Sample Size

The trial will enroll up to a maximum of 400 patients, randomized between two arms (treatment and control).

This phase II study has a flexible sample size. The purpose is to use a smaller sample size with very small or very large observed effect sizes, and a larger sample size where observed effect sizes are promising but more data are needed. For small observed effect sizes (with typically smaller sample sizes), the study results will have traditional phase II interpretations. However, for moderate/large observed effect sizes (with potentially larger sample sizes), the design is intended to provide sufficient evidence to justify regulatory conditional approval.

9.4 Analysis Populations

All randomized subjects will be analyzed according to the group in which they were randomized.

Intent-to-Treat (ITT): All randomized patients will be included in the intent-to-treat (ITT) population. The ITT population will serve as the primary analysis population for efficacy.

Safety Evaluable Population: All randomized patients who received any amount of study medication (APR-246, carboplatin, or PLD) will be considered evaluable for safety, regardless of the duration of treatment. This population will be used to summarize all safety parameters.

Efficacy Evaluable Population: All randomized patients with pre-treatment measurable disease by RECIST v1.1 who have at least one radiographic assessment after pre-treatment or discontinue study medication early due to disease progression and have a TP53 mutation will be considered evaluable for efficacy. The efficacy-evaluable population will be the secondary analysis population for efficacy.

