3.1.2 Secondary Objectives

- To assess the safety profile of the combined APR-246 and carboplatin/PLD chemotherapy regimen compared with carboplatin/PLD chemotherapy regimen alone.
- To evaluate potential biomarkers.
- To assess the biological activity in tumor and surrogate tissues.
- To compare quality of life of patients treated with these regimens.

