4.4 Treatment Allocation

Patients will be randomized in a 1:1 ratio to receive the carboplatin/PLD chemotherapy regimen with or without APR-246. The study treatment will not be blinded. Patients will be registered on-study as described in Section 4.2; the treatment arm will be automatically allocated during registration.

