6.4.2 Treatment Arm B: Carboplatin and PLD alone

Patients will receive carboplatin AUC 5 plus PLD at 30 mg/m^2 on Day 1 of each cycle. Treatment will be repeated every 28 days for a total of up to six cycles in the absence of disease progression or unacceptable toxicity. Supportive therapy will be given as per institutional standard of care. Patients randomized to Arm B will not receive APR-246.

Carboplatin Dosing

The dose of carboplatin will be calculated as per standard practice at that hospital. Patients will start at carboplatin with an AUC 5.

Pegylated Liposomal Doxorubicin Hydrochloride Dosing

The dose of PLD will be calculated based on the body surface of the patients at 30 mg/m^2 as per standard practice at that hospital.

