9.5.1 Safety Analysis

Safety data will be summarized for the safety evaluable population. These data will include adverse events and laboratory parameters. Adverse event terms will be coded using the Medical Dictionary for Drug Regulatory Activities (MedDRA®, version 16.0 or higher). Adverse events will be summarized by body system, preferred term, severity, and relationship to treatment. Serious adverse events, deaths, and AEs leading to early discontinuation of study drug will be summarized. Laboratory parameters will be summarized by maximum NCI-CTCAE-4.0 severity grade and also by change from pre-treatment to scheduled time points using descriptive statistics. Laboratory parameter listings will include the normal ranges for each parameter. Each value will be classified as falling above, below, or within the normal range.

Data summaries will include only treatment-emergent adverse events (TEAEs), defined as events occurring on or after Day 1 Cycle 1 up to and including 30 days after last dose.

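### Section 9.4 groups all randomised patients as randomised and does not exempt safety, so the safety tables should be stated to follow treatment actually received (small effect, cheap fix)

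*Combined protocol and SAP*

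**What the plan says.** Section 9.4 begins with one general sentence, "All randomized subjects will be analyzed according to the group in which they were randomized", and then defines three populations: intent-to-treat, safety evaluable and efficacy evaluable. The sentence stands above all three and is not placed under the intent-to-treat heading.

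The safety definition settles who is included: "All randomized patients who received any amount of study medication (APR-246, carboplatin, or PLD) will be considered evaluable for safety". It adds "This population will be used to summarize all safety parameters". It does not say in which treatment column a patient is reported.

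Section 9.5.1 names the population, "Safety data will be summarized for the safety evaluable population", and gives no grouping rule. None of the readable text elsewhere gives one. Appendix V is withheld from the public text, but sections 9.7 and 9.8.4 describe it as simulations and operating characteristics, so it is not an evident place for a safety grouping rule.

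The objective that depends on the grouping is in section 3.1.2: "To assess the safety profile of the combined APR-246 and carboplatin/PLD chemotherapy regimen compared with carboplatin/PLD chemotherapy regimen alone".

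**The concern.** Grouping as randomised is right for the intent-to-treat efficacy analysis. For safety the usual question is what happened to patients who received the drug, and there the same rule can attribute events to a drug the patient never had. Because receipt of any one of three drugs admits a patient to the safety set, two kinds of patient can land in the wrong column:

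- an Arm B patient given APR-246 by mistake, who stays under control;
- an Arm A patient given carboplatin or PLD but no APR-246, who stays under the combination.

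An Arm A patient who received none of the three drugs is outside the safety set and raises no issue. An Arm A patient who began APR-246 and stopped early was exposed and is in the right column under either rule.

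At stake is the between-regimen safety comparison. Section 9.3 says that, for moderate or large effects, the design is meant to support conditional approval, so the safety tables may carry regulatory weight. Leaving the rule to be settled after the data are seen, in an open-label trial, would also make the choice post hoc.

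**Working it through.** The plan states no figure that depends on this rule, so there is nothing to reproduce. The check is a reading of the text followed by an illustration of size.

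**Inputs from the documents.** Allocation is 1:1 (section 4.4: "Patients will be randomized in a 1:1 ratio to receive the carboplatin/PLD chemotherapy regimen with or without APR-246"). The first interim analysis is at 150 patients (9.8.1), the earliest stop for predicted success is at 200 (9.8.3.1), and the maximum is 400 (9.3). Arms are therefore about 75, 100 or 200 patients. The safety set may be slightly smaller.

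**Weight of one patient in an arm.** 1/75 = 1.3%, 1/100 = 1.0%, 1/200 = 0.5%.

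**Expected effect on a risk difference.** Let a fraction *u* of Arm A have received no APR-246 and a fraction *v* of Arm B have received it. Let the event risk be *p1* with APR-246 and *p0* without, with misgrouping unrelated to prognosis. As randomised:

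- Arm A shows (1 − u)·p1 + u·p0
- Arm B shows (1 − v)·p0 + v·p1
- the difference is (1 − u − v)·(p1 − p0)

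The shrinkage factor is 1 − u − v. If *k* of *n* patients in each arm are misplaced, it is 1 − 2k/n.

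**Assumed values.** The documents give neither misgrouping counts nor event rates for the randomised part, so these are illustrations only.

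| Patients per arm | k = 1 | k = 2 | k = 4 |
|---|---|---|---|
| 200 | 1.0% shrinkage | 2.0% | 4.0% |
| 100 | 2.0% | 4.0% | 8.0% |
| 75 | 2.7% | 5.3% | 10.7% |

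With assumed risks of 30% and 5% and 200 per arm, the difference of 25.0 points becomes 24.75, 24.5 or 24.0 points for k = 1, 2 or 4.

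A second case assumes u = 3%, v = 1%, and risks of 60% and 10%:

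- Arm A: 0.97 × 0.60 + 0.03 × 0.10 = 58.5%
- Arm B: 0.99 × 0.10 + 0.01 × 0.60 = 10.5%
- difference: 48 points instead of 50, which matches (1 − 0.03 − 0.01) × 50 = 48

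**Rare serious events.** Two cases in exposed patients, shown as 2 against 0 by treatment received, would be shown as 1 against 1 if one of them were an Arm B patient given APR-246. That needs a coincidence. Suppose exactly one Arm B patient was exposed, all of Arm A was exposed, and the two cases fell at random among exposed patients. The chance that one of them is the misplaced patient is 2/201 = 1.0% with 200 per arm and 2/76 = 2.6% with 75 per arm. Both figures presuppose that such a patient exists.

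**After the change.** Grouping by actual exposure sets the shrinkage factor to 1 under the same assumptions. No efficacy figure changes.

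**The case against.** **The sentence may only introduce the intent-to-treat set.** It speaks of all randomised subjects and comes directly before the one population that contains all of them. On that reading safety grouping is merely unstated. This is a fair account of what the authors may have meant, but the safety set is itself drawn from randomised patients and nothing limits the sentence. Anyone programming from the text would group safety as randomised. On either reading the same clarification is needed.

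**The trial leaves little room for misgrouping.** Section 6.4.2 says "Patients randomized to Arm B will not receive APR-246", and section 4.4 says "The study treatment will not be blinded". The arm is allocated automatically at registration, APR-246 is accounted for patient by patient (6.2), and a course is four 6-hour infusions, so exposure in Arm B would be an overt error. In Arm A, APR-246 starts on Day 1 and chemotherapy follows on Day 4 (6.4.1), and section 6.5.1.1 treats the four days as one unit and delays both if Day 1 haematology would prevent chemotherapy. A chemotherapy-only Arm A patient in the safety set should be unusual. This stands, and it is why the size is small.

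**A reader might infer that every misplaced patient biases toward no difference.** That is not so. The direction holds in expectation, for events that APR-246 raises and if misgrouping is unrelated to prognosis. An unexposed Arm A patient who has an event adds to the Arm A count and moves the comparison the other way.

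**A reader might also infer that a harm signal could be lost.** The documents do not support that. Causality is recorded for each adverse event (7.3.3.3, 7.3.3.4), summaries are split by relationship to treatment (9.5.1), serious events are reported individually within 24 hours (7.3.4), and the IDMC reviews cumulative serious events (1.5). A related serious event in a control patient given APR-246 would probably be noticed.

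**Grouping by treatment received gives up some randomised comparability.** If APR-246 was withheld from frailer Arm A patients, their events would move to control, which could itself understate harm. This stands as a real cost of the change.

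**Conclusion.** The point holds as a defect of wording with a small expected effect. Section 9.4 states a general as-randomised rule, and neither the safety definition nor section 9.5.1 provides an exception. Followed literally, it puts any patient whose APR-246 exposure differs from assignment in the wrong safety column. For events that APR-246 increases, the expected direction is toward hiding harm.

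One patient is 0.5 percentage points of an arm at 400 patients, 1.0 at 200 and 1.3 at 150. The shrinkage figures rest on assumed misgrouping counts and event rates and on misgrouping being unrelated to prognosis. The documents give no expected frequency, and the conduct of the trial suggests very few such patients.

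The point should not be read as showing a material bias in the safety comparison. Section 9.5.1 plans descriptive summaries only, with no safety test or threshold tied to this grouping. It is a cheap improvement of low severity.

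**What to change.** Make two changes to section 9.4.

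1. Limit the opening sentence to efficacy, for example: *For efficacy analyses, patients are kept in the arm assigned at randomisation.*
2. Add to the Safety Evaluable Population, for example: *Safety is summarised by treatment actually received. Patients who received any APR-246 are reported under APR-246 plus carboplatin/PLD, and all others under carboplatin/PLD alone. Patients whose actual and randomised groups differ are listed.*

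The listing lets a reader see whether reassigned patients were frailer and whether moving their events alters the comparison.

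The cost is two sentences. Treatment details and deviations already go into the eCRF and accountability records (5.4, 6.2). The intent-to-treat analysis, the stratified logrank test, its significance level, the sample size and trial conduct are unchanged.

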9.5 Statistical Methods

All demographic data and disease-related characteristics will be summarized using descriptive statistics (count and percent, mean, median, standard deviation, minimum, maximum), separately for phase Ib and phase II parts of the study.

9.5.1 Safety Analysis

Safety data will be summarized for the safety evaluable population. These data will include adverse events and laboratory parameters. Adverse event terms will be coded using the Medical Dictionary for Drug Regulatory Activities (MedDRA®, version 16.0 or higher). Adverse events will be summarized by body system, preferred term, severity, and relationship to treatment. Serious adverse events, deaths, and AEs leading to early discontinuation of study drug will be summarized. Laboratory parameters will be summarized by maximum NCI-CTCAE-4.0 severity grade and also by change from pre-treatment to scheduled time points using descriptive statistics. Laboratory parameter listings will include the normal ranges for each parameter. Each value will be classified as falling above, below, or within the normal range.

Data summaries will include only treatment-emergent adverse events (TEAEs), defined as events occurring on or after Day 1 Cycle 1 up to and including 30 days after last dose.

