7.3.3.2 Follow-up of Unresolved Adverse Events

All AEs should be followed until they are resolved or until the end of treatment (EoT) visit, whichever comes first. All AEs that are still ongoing after the EoT visit, should be followed on a regular basis, according to the Investigator's clinical judgment, until the event has resolved or until the Investigator assesses it as chronic and all queries have been resolved. After the EoT visit, AEs that are unrelated to APR-246 (serious or non-serious) or related but not serious, do not require further recording in the eCRF. For related SAEs that have been resolved, the event resolved date and the outcome of resolved or resolved with sequelae, as appropriate, should be recorded on the eCRF and the SAE Report Form. The Sponsor retains the right to request additional information for any patient with ongoing AE(s) at the end of the study, if judged necessary.

If an Investigator learns of any SAEs, including death, at any time following 30 days after the last administration of study treatment and he/she considers there is a reasonable possibility that the SAE is related to the study treatment, the Investigator should notify Theradex® Safety Desk.

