7.3.3.3 Variables

The following variables will be collected for each AE:

- AE diagnosis/description
- The date the AE started and stopped
- CTCAE version 4.0 grade
- Whether the AE is serious or not and the reason(s) it is serious
- Investigator causality rating against the investigational product (yes or no)
- Action taken with regard to study treatment
- Outcome

For SAEs other variables will be collected including treatment given for the event.

It is important to distinguish between serious and severe AEs. Severity is a measure of intensity whereas seriousness is defined by the criteria in Section 7.3.2. An AE of severe intensity need not necessarily be considered serious. For example, nausea that persists for several hours may be considered severe nausea, but not a SAE. On the other hand, a stroke that results in only a limited degree of disability may be considered a mild stroke but would be a SAE.

The grading scales found in the current National Cancer Institute CTCAE version 4.0 will be utilized for all events with an assigned CTCAE grading. For those events without assigned CTCAE grades, the recommendation in the CTCAE criteria that converts mild, moderate, and severe events into CTCAE grades should be used. A copy of the current CTCAE version can be downloaded from the Cancer Therapy Evaluation Program website (<http://ctep.cancer.gov>).

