7.3.3.10 Handling of Deaths

All deaths that occur during the study, or within the 30-day follow-up period after the administration of the last dose of investigational product, should be reported as follows:

- Death, which is unequivocally due to disease progression, should be communicated to the study monitor at the next monitoring visit and should be documented in the eCRF module, but should not be reported as a SAE during the study.
- Where death is not clearly due to disease progression of the disease under study the AE causing the death should be reported to the Theradex® Safety Desk as an SAE within 24 hours. The report should contain a comment regarding the co-involvement of progression of disease, if appropriate, and should assign a single primary cause of death together with any contributory causes.
- Deaths with an unknown cause should always be reported as a SAE but every effort should be made to establish a cause of death. A post-mortem may be helpful in the assessment of the cause of death, and if performed a copy of the post-mortem results (with translation of important parts into English) should be reported in an expedited fashion to the Theradex® Safety Desk within the usual timeframes.

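### Related SAEs starting more than 30 days after last dose are requested by 7.3.3.2, but on the literal TEAE-only rule in 9.5.1 they enter no planned adverse event summary

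*Combined protocol and SAP*

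**What the plan says.** All references are to the combined protocol and SAP.

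**What is requested.** Routine AE collection runs from consent to 30 days after the last study treatment (7.3.3.1). Section 7.3.3.2 goes further for one category. It begins "If an Investigator learns of any SAEs, including death" and continues "at any time following 30 days after the last administration of study treatment and he/she considers there is a reasonable possibility" of a relation to study treatment; in that case the safety desk is to be notified. No upper time limit is given.

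**What is summarised.** Section 9.5.1 says "Serious adverse events, deaths, and AEs leading to early discontinuation of study drug will be summarized", with no window in that sentence. A later sentence in the same section restricts the outputs: "Data summaries will include only treatment-emergent adverse events (TEAEs", and these are "defined as events occurring on or after Day 1 Cycle 1 up to and including 30 days after last dose". No exception is made for serious, related or fatal events.

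**Causality.** Section 7.3.3.3 lists "Investigator causality rating against the investigational product (yes or no" among the AE variables, and 6.4.2 states "Patients randomized to Arm B will not receive APR-246". However, 7.3.3.4 words the causality question in terms of the study treatment, and for SAEs it also asks about other medication and study procedures.

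**Deaths.** Section 7.3.3.10 sets reporting rules, including assignment of a cause, for "All deaths that occur during the study, or within the 30-day follow-up period after the administration of the last dose of investigational product". Overall survival in 9.5.2.2 counts every death.

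**The concern.** The plan asks sites for a specific kind of late safety report and then gives it no stated place in the study outputs. Comparing safety with chemotherapy alone is a secondary objective (3.1.2), and for moderate or large effects the design is meant to support conditional approval (9.3). A reader of the safety account would expect related serious harms that were notified to appear in it.

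The protocol itself names harms that need not arise within 30 days. Section 7.3.3.9 treats new cancers as AEs that will usually be serious, and 6.5.4 refers to irreversible cardiac damage with PLD. Survival follow-up continues until death (footnotes to Tables 9 and 10), so an investigator may well learn of such an event.

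What is at stake is the completeness of a descriptive safety report. The primary analysis is not involved.

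**Working it through.** The documents state no figure to reproduce. The check sets the reporting rule beside the summary rule.

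**Step 1. Sort events by onset.**

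| Event | Requested by 7.3.3.2? | TEAE under 9.5.1? | In a planned AE summary? |
|---|---|---|---|
| Related SAE, onset by day 30 after last dose, learned of later | Yes | Yes | Yes |
| Related non-fatal SAE, onset after day 30 | Yes | No | No, on the literal rule |
| Related fatal SAE, onset after day 30 | Yes | No | No, on the literal rule; the death counts in OS, and in PFS if no progression came first |
| Unrelated or non-serious event, onset after day 30 | No | No | No, and none was asked for |

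The gap is rows two and three.

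**Step 2. Look for another output.** The only listings named in 9.5.1 are for laboratory parameters. Section 9.5.2.2 covers efficacy. Section 1.5 gives the IDMC reports on cumulated SAEs, which serve its recommendations and are not a study output. No other section plans an AE table or listing.

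**Step 3. When the window closes, for six on-time cycles.**
- Cycle 6 Day 1 = 5 × 28 + 1 = Day 141, the last dose in Arm B. Cycle 6 Day 4 = Day 144, the last dose in Arm A.
- Adding 30 days gives Day 171 (Arm B) and Day 174 (Arm A).
- The earliest end-of-treatment visit is day 28 of cycle 6 = 140 + 28 = Day 168. The first follow-up visit is 2 months later (taken as 61 days) ± 2 weeks, so at the earliest 168 + 61 − 14 = Day 215.
- That is 215 − 174 = 41 days (Arm A) or 215 − 171 = 44 days (Arm B) after the window closes.

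If treatment stops early, the first follow-up visit is still at least 61 − 14 = 47 days after last dose. Every scheduled follow-up visit therefore falls outside the window, and 7.2.6 lists no adverse event enquiry at those visits. Capture of late SAEs is passive.

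**Step 4. Size.** The documents give no late-event rate, so the number of affected patients cannot be estimated. As pure illustration, assume that 0.5% to 3% of patients have a notified late related SAE. Expected patients per arm are n × p, and the chance of at least one is 1 − (1 − p)^n. Arm sizes are half of total enrolment, an upper bound for the safety evaluable population.

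| Patients per arm | Expected | Chance of at least one |
|---|---|---|
| 75 (accrual stopped at 150) | 0.4 to 2.3 | 31% to 90% |
| 100 (stopped at 200) | 0.5 to 3 | 39% to 95% |
| 200 (maximum of 400) | 1 to 6 | 63% to 99.8% |

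The width of these ranges shows how little can be said about size. They follow from the assumed rate alone.

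**The case against.** The strongest reply is that 9.5.1 promises summaries of SAEs and deaths in a sentence without a window, so the authors may have meant those tables to extend past day 30. This stands as an ambiguity, and it must be read the same way for SAEs as for deaths, since one clause names both. It does not settle the matter, because the TEAE-only sentence follows in the same section and is worded to cover data summaries in general.

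Second, the TEAE window ends when routine AE collection ends, so keeping passively reported events out of the comparative tables is defensible. This stands, and it is the reason to leave those tables alone. It does not explain why requested reports have no separate place.

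Third, 9.5.1 plans no AE listing of any kind, so it does not forbid one for late SAEs. That is true, but nothing commits the sponsor to produce it.

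Fourth, there are other routes: OS, the death reporting in 7.3.3.10, eCRF recording of SAEs under 7.3.4, and IDMC review. OS holds neither non-fatal SAEs nor relatedness. Sections 7.3.3.10 and 7.3.4 govern reporting and recording, and the period set in 7.3.4 ends at 30 days. IDMC review is monitoring.

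Fifth, a by-arm output filtered by unblinded causality judgement invites a comparison that it cannot support. This stands and is met by a descriptive listing with a stated caveat.

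A reader might also infer from 7.3.3.3 that late SAEs in Arm B could not be classed as related, since that arm receives no APR-246. The documents do not support this: 7.3.3.2 and 7.3.3.4 both refer to study treatment, and for SAEs 7.3.3.4 also covers other medication.

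**Conclusion.** The point holds as a minor, inexpensive improvement. On the literal TEAE-only rule, a related SAE with onset more than 30 days after last dose is notifiable and appears in no planned adverse event summary. The windowless sentence on SAEs and deaths leaves the intention unclear for both.

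The conclusion rests on reading the word that limits the summaries to TEAEs as it stands, and on finding no other planned AE output. The number of events is unknown. No primary conclusion, power figure or Type I error rate is affected.

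Two stronger readings should be resisted. One is that late-reported SAEs in general are lost; those with onset inside the window remain TEAEs and are summarised. The other is that a large share of harm goes unreported because roughly half of the first year lies outside the window: (365 − 174)/365 = 52% in Arm A and (365 − 171)/365 = 53% in Arm B. Those are shares of time, and the documents give no basis for turning them into shares of harm.

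**What to change.** Leave the TEAE tables unchanged and add to 9.5.1:

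> SAEs, including deaths, with onset more than 30 days after last dose that are considered related to study treatment (APR-246, carboplatin or PLD, per the causality question in 7.3.3.4) will be listed by arm in the safety evaluable population, with the number of patients affected, onset day, cause and outcome. This output is descriptive only; capture is passive and causality is open-label, so counts are not rates and will not be formally compared.

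Naming the three drugs makes the criterion the same in both arms.

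The cost is one extra output. Late reports go to the safety desk, so they may have to be transferred to the trial database. The counts will be incomplete, because no scheduled enquiry supports them.
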